8.3 Allowed Medications

Medications, other than those that are prohibited or restricted (Section 8.1 and Section 8.2), such as antihistamines, leukotriene antagonists, and sodium cromolyn are allowed during the study and, unless required due to unforeseen medical necessity, doses and/or dietary modifications are to remain stable.

All types and formulations of vaccines approved by FDA or other regulatory authority for the prevention of COVID-19 may be administered before, during, or after the study. The vaccine should not be administered within 7 days before and within 7 days after the administration of study drug so that any side effects caused by either of the 2 medications can be more easily determined.

Systemic or swallowed corticosteroids with a dose of ≤ 10 mg/day prednisone or equivalent being used at the time of study entry are acceptable as long as the dose remains stable throughout screening and during the study.

Short courses or a single use of corticosteroid therapy at doses of ≤ 10 mg/day of prednisone or equivalent due to unforeseen medical necessity for conditions other than the disease under study will be allowed at the discretion of the Investigator provided that the corticosteroids are discontinued prior to Study Week 21. Consideration should be given to alternative therapies whenever possible.

Swallowed or systemic corticosteroids at a dose of >10 mg are not considered prohibited under the following circumstances:

- Systemic corticosteroids given within 24 hours of the start of an infusion when medically necessary for the treatment of an IRR.
- A single dose of IV corticosteroid given during the EGD to minimize AE associated with anesthesia (e.g., nausea and vomiting after anesthesia).
- Premedication with prednisone prior to Dose 1 in the double-blind period and Dose 1 in the OLE period, as required by the protocol.
- Premedication with a systemic corticosteroid (for any dose other than Dose 1 in the double-blind period and Dose 1 in the OLE period), which has been preapproved by the Medical Monitor prior to dosing.

All medication used during the screening period and throughout the study will be documented in the CRF. Any allowed medications that are taken must remain stable throughout the study.

Medications administered for the EGD and colonoscopy are allowed. Medications administered for bowel preparation prior to colonoscopies are also allowed.

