15.6 Efficacy Analysis

15.6.1 Primary Efficacy Endpoint Analysis

The first co-primary endpoint will be analyzed using Fisher's exact test. Patients who experience an ICE, i.e., exit the study prematurely or initiate prohibited or restricted medication, prior to end of Week 24 will be treated as non-responders. Proportion of responders and the associated 95% confidence interval (CI) will be presented for each treatment group. The between-group difference and the associated 95% CI will also be computed and presented. Sensitivity analysis may be carried out using the Cochran-Mantel-Haenszel (CMH) test stratified by the randomization stratification factor (baseline TSS <28 vs ≥ 28) to assess robustness of Fisher's exact test results.

The rationale for specifying Fisher's exact test for the primary analysis as opposed to specifying the CMH test is because when a stratum has 100% response for 1 treatment group and 0% response for another treatment group, the CMH test may lose efficiency or not be computable. This is evident from the Phase 2 study outcome.

The second co-primary endpoint will be analyzed using mixed model for repeat measures (MMRM) with treatment, week, treatment-by-week interaction, and baseline TSS-by-week interaction as fixed factors; gender and baseline TSS (continuous) as covariates; and study site (with pooling by geographic location) as random effect. If the model does not converge with pooled sites as a random effect, it will be simplified with pooled site as a fixed effect. Details about the method for pooling sites will be provided in the statistical analysis plan (SAP).

The weekly TSS is calculated as the average of the daily TSS. Weekly TSS will be set to missing if >3 daily TSS are missing. Baseline TSS will be the average of the last 2 weeks of daily TSS collected prior to the first infusion. The model variance-covariance matrix will be unstructured. However, if computation does not converge, the matrix will take the form of Toeplitz, autoregressive, or compound symmetry, whichever converges first.

Data on patients who experience an ICE, i.e., exit the study prematurely or initiate prohibited or restricted medications, prior to the end of Week 24 will be set to missing. If it is evident that the

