## 9.2 Appendix 2: Intercurrent Events

A. Use of any of the following prohibited medications during the course of the study as described

- 1) Immunosuppressive or immunomodulatory drugs (e.g., IL-5 modulators, i.e., benralizumab, reslizumab, mepolizumab; IL-4 and IL-13 antagonists, i.e., dupilumab; calcineurin inhibitors, i.e., cyclosporin, tacrolimus; mTOR inhibitors, i.e., sirolimus, everolimus; anti-metabolites, i.e., azathioprine, methotrexate, 6-mercaptopurine, leflunomide, mycophenolate mofetil; alkylating agents, i.e., cyclophosphamide; TNF inhibitors, i.e., infliximab, adalimumab; anti-IgE antibodies, i.e., omalizumab; and eosinophil-depleting drugs, i.e., pramipexole.
  - a) Use at any point during the study.
- 2) Glucocorticoids
  - a) Initiation of any course of treatment or single use of systemic or swallowed corticosteroids at a dose of  $>10$  mg/day prednisone or equivalent starting at Week 21 and through the end of Week 24. This does not include use of corticosteroids given as pre-infusion prophylaxis or treatment of IRR.

B. Use of restricted medications outside the protocol-defined specifications

- 1) Glucocorticoids
  - a) Discontinuation of a previously stable dose of systemic or swallowed corticosteroids ( $\leq 10$  mg/day prednisone or equivalent) after the screening period.
  - b) Initiation of a new course of systemic or swallowed corticosteroids ( $\leq 10$  mg/day prednisone or equivalent) following the screening period and continuing to at least study Week 21 (within 2 weeks of efficacy assessment at Weeks 23 and 24).
- 2) Proton Pump Inhibitors
  - a) Discontinuation of a previously stable dose of an oral PPI after the screening period and before the end of Week 24.
  - b) Initiation or increase in the dose of an oral PPI following the screening period and continuing to at least study Week 21 (within 2 weeks of efficacy assessment at Weeks 23 and 24).
- 3) Sodium cromolyn
  - a) Discontinuation of a previously stable dose of sodium cromolyn after the screening period and before the end of Week 24

- b) Initiation or increase in the dose of sodium cromolyn following the screening period and continuing to at least study Week 22 (within 1 week of efficacy assessment at Weeks 23 and 24).

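### SAP Appendix 2 omits Protocol 8.3's allowance for a single IV steroid dose at the EGD, so an endpoint scope on Days 166–168 can itself create an intercurrent event and a histology non-response

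*SAP*

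**What the plan says.** **The ICE rule.** SAP Appendix 2, A.2.a (Glucocorticoids), counts as an ICE "Initiation of any course of treatment or single use of systemic or swallowed corticosteroids at a dose of" more than 10 mg/day "prednisone or equivalent starting at Week 21 and through the end of Week 24". It then states two exemptions: "This does not include use of corticosteroids given as pre-infusion prophylaxis or treatment of IRR".

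**The medication rule.** Protocol 8.3 opens a list with "Swallowed or systemic corticosteroids at a dose of >10 mg are not considered prohibited under the following circumstances". The list has four items: steroid treatment of an infusion-related reaction (IRR), the required Dose 1 premedication, premedication preapproved by the Medical Monitor, and "A single dose of IV corticosteroid given during the EGD to minimize AE associated with anesthesia (e.g., nausea and vomiting after anesthesia". The same section adds that drugs given for the EGD and colonoscopy are allowed.

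**Timing.** SAP Table 2 counts study weeks in blocks of seven days from Day 1. The schedule of assessments in both documents puts the endpoint EGD and colonoscopy on Day 169 ± 3.

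**Consequence of an ICE.** Under Protocol 15.6.1, patients with an ICE "prior to end of Week 24 will be treated as non-responders". SAP 5.4.1 sets to missing any eosinophil count collected after an ICE and, when no other post-baseline count exists, scores the subject a treatment failure. SAP 5.4.2 sets diary scores collected after an ICE to missing.

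**The concern.** The two lists do not match. The SAP's exemptions cover the protocol's IRR and premedication items but not the dose given at the EGD. Because the EGD window straddles the end of Week 24, the omission has a practical effect: whether a patient has an ICE depends on which permitted day the scope was booked.

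The rationale at the end of SAP Appendix 2 is that a drug taken close enough to the evaluation could alter symptoms or histology. A dose given during the procedure that collects the biopsies does not fit that rationale. Yet ICE status feeds both co-primary endpoints, and also the secondary endpoints in SAP 2.2 that use the Week 24 eosinophil count. Drugs given at the EGD must be recorded (Protocol 8 and 12.13), so the data that would trigger the rule will be in the database.

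**Working it through.** **Calendar.** Week k runs from Day 7(k−1)+1 to Day 7k.
- Week 21: 7×20+1 = Day 141 to 7×21 = Day 147.
- Week 23 starts at 7×22+1 = Day 155. Week 24 is 7×23+1 = Day 162 to 7×24 = Day 168. Weeks 23–24 are therefore Days 155–168, which reproduces the range given in Protocol 11.2.1.
- A.2.a window: Days 141–168.
- EGD window: 169 ± 3 = Days 166–172.
- Overlap: Days 166, 167 and 168, i.e. 3 of 7 permitted days. Days 169–172 are in Week 25, outside the rule.

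**Histology.** Take a patient given an IV steroid above the threshold at a Day 166–168 scope.
- Protocol 15.6.1: an ICE before the end of Week 24 means non-responder, whatever the order of events that day.
- SAP 5.4.1: the count is lost only if the biopsy is regarded as collected after the ICE. The SAP has no rule for ordering two events in one procedure. If the count is lost and no other post-baseline count exists, the patient is a treatment failure.

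**Symptom score.** SAP 5.4.2 needs at least 4 of 7 daily scores for a weekly value, and both weekly values for the Weeks 23–24 average. Assume every diary is completed and that the Protocol synopsis rule excluding the day before and the day of colonoscopy also applies at Week 24.

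| Scope day | Week 24 diaries left, no ICE | Left with an ICE from the scope day |
|---|---|---|
| 166 | 162, 163, 164, 167, 168 = 5 | 162–164 = 3 (week missing) |
| 167 | 162–165, 168 = 5 | 162–165 = 4 |
| 168 | 162–166 = 5 | 162–166 = 5 |

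Only the Day 166 scope loses the week outright. A Day 167 scope has no diary to spare.

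**Effect on the histology comparison.** Inputs: planning rates 0.6 and 0.1, 40 per group (Protocol 15.1, SAP 3.5); two-sided 0.05 (SAP 5.8). Exact Fisher power at these inputs is 99.8%, consistent with the plan's statement of more than 90%. Let f be the share of patients in each arm who are wrongly failed. The rates become 0.6(1−f) and 0.1(1−f), and the difference becomes 0.5(1−f). The values of f are assumptions; the documents give none.

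| f | AK002 | Placebo | Difference | Fisher power, 40 per arm |
|---|---|---|---|---|
| 0 | 0.600 | 0.100 | 0.500 | 99.8% |
| 5% | 0.570 | 0.095 | 0.475 | 99.7% |
| 10% | 0.540 | 0.090 | 0.450 | 99.4% |
| 20% | 0.480 | 0.080 | 0.400 | 98.3% |
| 43% (3/7) | 0.343 | 0.057 | 0.286 | 88.8% |

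The last row is an extreme: every patient receives the steroid and scope days are spread evenly over the window.

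**The case against.** **The heading may already exempt the dose.** A.2.a sits under "Use of any of the following prohibited medications during the course of the study as described", and Protocol 8.3 says the EGD dose is not prohibited. The SAP supersedes the protocol's statistical methods, not its classification of drugs. On that reading the dose was never an ICE. This is a fair reading, and it is why the problem is a conflict rather than a settled error of outcome. But if the heading imported Protocol 8.3, the exemption sentence in A.2.a would be unnecessary, because 8.3 already covers IRR treatment and premedication. Naming two exemptions implies that a third is not exempt. Two programmers could code this differently.

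**A reader might infer that such a patient is certain to be failed.** The documents do not support that. SAP 4.2.5 applies ICE handling from the point at which the event occurs, SAP 5.4.1 voids only counts collected afterwards, and the same-day order is undefined. "Can be scored" is as far as it goes.

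**A reader might also infer that the IRR exemption is too wide and biases one arm.** A.2.a sets no time limit on IRR steroids, whereas Protocol 8.3 speaks of "Systemic corticosteroids given within 24 hours of the start of an infusion when medically necessary for the treatment of an IRR". But the SAP wording follows Protocol 8.2, which has no limit either, so the difference already exists within the protocol. The documents give no IRR rates by arm and no frequency of prolonged courses, and Protocol 2.3 reports fewer adverse events at later infusions. Part of the Dose 6 window (Days 138–140) is in Week 20, before A.2.a applies. All that stands is that Protocol 8.2 (no limit) and Protocol 8.1, 8.3 and 13.4 (24 hours) need to be reconciled.

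**The symptom effect is narrow.** This is correct. It is outright only for a Day 166 scope, and it depends on the colonoscopy-day exclusion, which SAP 5.4.2 says only will be taken into consideration at Week 24. The primary MMRM tolerates a missing final value under MAR.

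**Conclusion.** The rule is wrong as written, at moderate severity. As they stand, SAP A.2.a and Protocol 8.3 disagree on a single IV steroid dose at the EGD, and the disagreement bites on 3 of the 7 permitted endpoint scope days. It can turn a histologic responder into a non-responder on a co-primary endpoint because of the scope date. For a Day 166 scope it can also remove the Weeks 23–24 symptom score.

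Its frequency cannot be derived from the documents: they give neither how often an IV steroid is used at the EGD, nor its dose, nor the spread of scope days. Protocol 8.3 does list it among doses above 10 mg.

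A reader might infer that the histology result is at risk or that the treatment effect is inflated. Neither follows. With equal shares affected in both arms, the error shrinks the difference, and at 40 per arm exact power stays at 98% or more up to a 20% share. The Evaluable population may be smaller than 40 per arm. At an assumed 25 per arm, power is 96.0% with no one affected and 91.7% at a 10% share. What is at stake is a correctly classified outcome and an undistorted estimate.

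**What to change.** Before unblinding, reconcile SAP Appendix 2 A.2.a with Protocol 8.3 by adding the single IV corticosteroid dose given during the EGD to the ICE exemptions. State also that a steroid given during the Week 24 EGD voids neither the biopsy from that EGD nor the diary scores that follow it.

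The cost is a sentence or two in Appendix 2. No new data are needed, since EGD dates and procedure medications are already collected. In the same revision, the sponsor should reconcile the protocol's own passages on the time limit for IRR steroids (8.2 against 8.1, 8.3 and 13.4).

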7.5 Exclusion Criteria

Patients will be excluded from the study if they meet any of the following criteria:

- 1) Use of systemic or topical corticosteroids exceeding the equivalent of 10 mg/day prednisone within 4 weeks prior to the screening visit.
- 2) Baseline endoscopic biopsy with ≥ 30 eosinophils/hpf in 5 hpf in the gastric mucosa as determined by central histology assessment of biopsies collected during the screening EGD.
- 3) Change in the dose of corticosteroids (systemic or topical), PPI, leukotrienes, or diet therapy within 4 weeks prior to the screening visit.
- 4) Treatment with any immunosuppressive or immunomodulatory drugs that may interfere with the study within 12 weeks prior to the screening visit.
- 5) Prior exposure to AK002 or known hypersensitivity to any constituent of the study drug.
- 6) Active *H. pylori* infection as confirmed by a stool antigen test for *H. pylori*.
- 7) History of inflammatory bowel disease, other chronic inflammatory diseases in the colon (with the exception of eosinophilic colitis), celiac disease, achalasia, or esophageal surgery.
- 8) History of bleeding disorders and/or esophageal varices considered to be significant by the Investigator.
- 9) Other significant causes of gastric and/or duodenal eosinophilia or eosinophilic granulomatosis with polyangiitis (EGPA).
- 10) Confirmed diagnosis of hypereosinophilic syndrome (HES).

- 11) Women who are pregnant, breastfeeding, or planning to become pregnant while participating in the study.
- 12) Presence of an abnormal laboratory value considered to be clinically significant by the Investigator.
- 13) Any disease, condition (medical or surgical), or cardiac abnormality, which, in the opinion of the Investigator, would place the patient at increased risk.
- 14) History of malignancy, except carcinoma in situ, early-stage prostate cancer, or non-melanoma skin cancers. However, patients with cancers that have been in remission for more than 5 years and are considered cured can be enrolled.
- 15) Treatment for a clinically significant helminthic parasitic infection within 6 months of screening.
- 16) Positive helminthic infection on ova and parasite (O&P) test.
- 17) Seropositive for *Strongyloides stercoralis* at screening.
- 18) Seropositive for HIV or hepatitis at screening, except for vaccinated patients or patients with past but resolved hepatitis, at screening. See [Appendix 12](#).

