11.2.6 Baseline Diet Assessment and Compliance

During the screening visit the Investigator or designee will ask the patient a standardized series of dietary assessment questions ([Appendix 3](#)). This baseline diet assessment involves questions regarding food behavior and patterns, as well as types of foods generally avoided, and will serve to establish the baseline diet. Answers will be documented in the source documents and recorded in the eCRF.

This baseline diet should be maintained, as much as possible, throughout the course of the study, even if symptoms improve. Compliance with the baseline diet will be assessed at study visits on Days 1, 15, 29, 57, 85, 113, 141, 176, 197, and 225 or 35,56, and 84 (± 3) days after last dose of study drug if ET. Whether or not the patient has maintained the baseline diet and what deviations were made, if applicable, should be documented in the source documents and the eCRF.

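### The SAP's intercurrent-event list omits an increase in a stable low-dose corticosteroid, and any course above 10 mg/day begun before Week 21

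*SAP*

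**What the plan says.** Protocol 4.5.4 and SAP 4.2.4 name two kinds of ICE: leaving the study early, and using prohibited or restricted medication. Both defer the detail, and SAP 4.2.4 points to SAP Appendix 2 (section 9.2).

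On corticosteroids, Appendix 2 has three items:

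- A.2.a: "Initiation of any course of treatment or single use of systemic or swallowed corticosteroids at a dose of" more than 10 mg/day prednisone equivalent, starting from Week 21 to the end of Week 24. Infusion prophylaxis and treatment of infusion reactions are exempt.
- B.1.a: "Discontinuation of a previously stable dose of systemic or swallowed corticosteroids" at or below 10 mg/day, after screening.
- B.1.b: "Initiation of a new course of systemic or swallowed corticosteroids" at or below 10 mg/day after screening, continuing to at least Week 21.

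For PPI, item B.2.b reads "Initiation or increase in the dose of an oral PPI following the screening period and continuing to at least study Week 21". Item B.3.b has the same form for sodium cromolyn, with Week 22.

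The appendix then gives its reasons. Steroids and PPI can affect both histology and reported symptoms, so a patient on either at screening has to stay on a stable dose if change from baseline is to be interpretable. Protocol 8.3 likewise accepts low-dose steroids present at entry only while the dose stays stable. Protocol 8.2 classes steroids above 10 mg/day for EoD as rescue therapy whenever they are used.

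**The concern.** Only data after a listed ICE are removed. Under SAP 5.4.1, later eosinophil counts are set to missing, and a patient with no usable earlier post-baseline count becomes a failure. Under SAP 5.4.2, later daily PRO scores are set to missing. A steroid change outside the list triggers neither rule, so both co-primary outcomes are taken as observed under intensified background therapy.

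The estimand question in SAP 4.2.5 asks what improvement to expect on study medication when no further medication that may affect the disease is added. A sustained steroid increase departs from that question, on the SAP's own account of what steroids do. If increases are more common in one arm, the estimated difference mixes the drug effect with steroid effect. If the gap is noticed only after unblinding, classifying these patients becomes a matter of discretion.

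**Working it through.** **Step 1: text check.** Appendix 2 items, by type of post-screening change:

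| Therapy | Stop | Start | Increase |
|---|---|---|---|
| PPI | B.2.a | B.2.b (continuing to Week 21) | B.2.b |
| Sodium cromolyn | B.3.a | B.3.b (continuing to Week 22) | B.3.b |
| Steroid ≤10 mg/day | B.1.a | B.1.b (continuing to Week 21) | not listed |
| Steroid >10 mg/day | – | A.2.a, only if begun in Weeks 21–24 | A.2.a on a natural reading, same weeks only |

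Two cells are open:

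1. A rise within the range up to 10 mg/day at any time, for example 2 to 10 mg/day, even if held through Week 24. The appendix's rationale for steroids also speaks only of starting or of a new course.
2. A course above 10 mg/day begun before Week 21 and still running in Weeks 23–24. B.1.b does not reach it, being limited to 10 mg/day or less. A.2.a does not, because it is tied to initiation from Week 21.

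**Step 2: the plan's own figure.** Inputs from SAP 3.5 and 5.8: 40 per arm, difference 7.4, SD 12.5, two-sided 0.05. SE = 12.5 × √(2/40) = 2.795; 7.4/2.795 = 2.648; 2.648 − 1.960 = 0.688; power = Φ(0.688) = 75.4% (74.4% with the t distribution). The stated 80% is not reproduced; that is a separate matter and does not bear on this point. For histology (0.6 v 0.1, Fisher's exact test) power is 99.8%, consistent with the stated figure above 90%.

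**Step 3: illustrative size.** The documents give no frequency or effect of steroid intensification, so q and b are assumptions. Let q be the excess proportion of placebo patients who intensify and b the TSS points each gains. The expected difference is 7.4 − q × b, and power is recomputed as in Step 2. One patient in 40 moves an arm mean by b/40, which is 0.1 point for b = 4 and 0.3 for b = 12.

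| Excess q | Difference if excess on placebo (b = 4 to 12) | Power | Difference if excess on AK002 |
|---|---|---|---|
| 5% | 7.2 to 6.8 | 73% to 68% | 7.6 to 8.0 |
| 10% | 7.0 to 6.2 | 71% to 60% | 7.8 to 8.6 |
| 20% | 6.6 to 5.0 | 66% to 43% | 8.2 to 9.8 |

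For histology, suppose half of the intensifying placebo patients who would otherwise fail become responders. The placebo rate is then 0.1 + q × 0.9 × 0.5, that is 0.1225, 0.145 and 0.19, and Fisher power is 99.5%, 98.8% and 95.8%.

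**The case against.** Several points on the other side are fair.

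- **A.2.a does some of the work.** A rise above 10 mg/day starting in Weeks 21–24 is caught on a natural reading. A reader might infer that every steroid increase escapes the list; that goes too far.
- **The general category could be said to cover the rest.** Protocol 15.6.1 counts starting restricted medication before the end of Week 24, and Protocol 8.2 restricts use above 10 mg/day. But the SAP states that it supersedes the protocol's statistical methods, and Appendix 2 is where it sets the detail. For doses at or below 10 mg/day the general wording does not help, because Protocol 8.3 places them among allowed medications.
- **The affected group may be small.** The first gap needs a patient on low-dose steroid at entry who is raised but kept within 10 mg/day. This stands, and it points to the lower rows of the illustration.
- **A Per Protocol TSS analysis is planned.** It may drop such patients as major violators, but it is supplementary and its exclusion criteria are still to be set.

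A reader might also infer that diet and leukotriene changes are wrongly missing, since Exclusion 3 bars entry after "Change in the dose of corticosteroids (systemic or topical), PPI, leukotrienes, or diet therapy within 4 weeks prior to the screening visit" and Protocol 8.3 says "doses and/or dietary modifications are to remain stable". The documents do not support calling that an error. Exclusion 3 is an entry rule. The ICE category is prohibited or restricted medication, leukotriene antagonists are expressly allowed, diet is not a medication, and the stability rule excepts unforeseen medical necessity. The two-week washout behind Week 21 is estimated only for PPI and corticosteroids. Leaving these as observed is a debatable choice, not a contradiction.

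**Conclusion.** The point holds for corticosteroids. The list treats a raised steroid dose at or below 10 mg/day differently from a raised PPI or cromolyn dose, gives no reason, and so conflicts with its own stability rationale and with the estimand question. Separately, A.2.a and Protocol 8.2 do not agree on when use above 10 mg/day matters, and a course begun before Week 21 that runs into the endpoint window is unlisted.

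This rests on the text, not on a number. The size is unknown. On the assumptions shown, an excess of 5–10% in one arm moves the TSS difference by 0.2 to 1.2 points, which matters for an endpoint with little power to spare; histology remains robust. These figures use 40 per arm, and each patient weighs more if the Evaluable population is smaller.

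Two stronger inferences are not supported. One is that the gap favours a particular arm: the direction depends on which arm intensifies more, and the documents do not say. The other is that affected patients are scored as if on study drug alone: stable background therapy is permitted throughout, so the proper comparison is study drug plus stable background therapy.

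**What to change.** Before database lock, amend SAP Appendix 2:

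1. In B.1.b, cover both initiation and an increase in the dose of systemic or swallowed corticosteroids at or below 10 mg/day, with the existing Week 21 condition, so that it matches B.2.b. Make the same change in the rationale text.
2. Reconcile A.2.a with Protocol 8.2, and state how a course above 10 mg/day begun before Week 21 and continuing into the assessment window is classified, so that all such patients are handled alike. Which clinical rule should govern is for the sponsor to settle.

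The data are already collected: dose, dates and indication are recorded on the concomitant-medication form (Protocol 11.3.1). SAP 5.1 provides for amendments. The cost is a wording change and a few more patients who may be classed as having an ICE, so responder rates may be slightly lower and a few more late TSS values missing. No change to the list is needed for diet or leukotriene therapy on this ground.
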